1. Developing a novel technology-based intervention for anxiety and depressive symptoms among those receiving medication treatment for OUD.
2. Evaluating the feasibility of a technology-based intervention for anxiety and depressive symptoms among persons receiving treatment for OUD.
3. Evaluating the efficacy of a technology-based intervention for anxiety and depressive symptoms among persons with OUD.
4. Evaluating the efficacy of a technology-based intervention treating anxiety and depressive symptoms on cravings and opioid use among persons receiving medication treatment for OUD.

2. Objectives and Hypotheses

Aim 1: To test the feasibility and acceptability of the digital intervention designed to treat anxiety and depressive symptoms among persons receiving medication treatments for OUD.

Hypothesis 1: The digital intervention will show feasibility based on the ability to recruit participants (N = 40 within the digital intervention + medication treatment, N = 40 with medication treatment) and demonstrate acceptability of the application with greater than 50% of the intervention sessions completed on average by the treatment group.

Aim 2: To test the efficacy of a digital intervention targeting anxiety and depressive symptoms among persons receiving medication treatment for OUD. Sixty participants receiving medication treatment for OUD will be randomized to receive a digital intervention to treat anxiety and depression (N = 30) or care as usual (N = 30) for a total of four weeks.

Hypothesis 2: The digital intervention app group will experience (a) greater symptom reduction in anxiety and depressive symptoms (based on self-report measures) and (b) decreased opioid cravings and use across a four-week period (based on self-report measures and urine tests).

3. Study Design

Describe all study procedures, materials, and methods of data collection:

Recruitment. A population of 3000 adults who are receiving medication treatment for OUD will be recruited from an online study based on Google Adwords and Facebook advertisements as online recruitment has been shown to be a viable and cost-effective recruitment method for opioid users (Marshall et al., 2018).

We would also like to expand our recruitment efforts to Reddit sub-pages as well. Previous researchers looking at opioid addiction have had success posting in the Reddit forums and we would like to also recruit using this platform.

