Main Study: Participants will complete the main consent form. Participants will complete self-report assessments on their anxiety symptoms, depressive symptoms, opioid cravings, and opioid use behaviors. Participants will be randomized to a smartphone-based digital intervention or waitlist control condition. The control group can receive the intervention once they have completed the one-month follow up section of the study if they would like it. The digital intervention will be designed to treat participants' anxiety and depressive symptoms, and participants will be asked to use the intervention four times per week for four weeks (16 digital sessions). Participants will complete post measures and one-month follow-up measures on anxiety symptoms, depressive symptoms, opioid cravings, and opioid use behaviors. The Precision Dx12-panel test cups (manufactured by American Screening Complete Drug Test Solutions) will be mailed to participants. Participants will also be asked to complete five urine tests to detect substance use (amphetamines, barbiturates, benzodiazepines, cocaine, ecstasy, marijuana, methamphetamine, opioids, oxycodone, and propoxyphene) across the study (1 at pre-digital intervention, 1 during the digital intervention, 1 post-digital intervention, 1 between post and follow-up of the digital intervention, and 1 at the 1-month follow-up of the digital intervention). Participants will be instructed when to complete each urine test and will be asked to take a photo of the back the label of each test showing the results to the experimenters and to text these photos to a Google Voice Number maintained by the experimenters. Both the digital intervention group and the control group will receive the same follow-up assessments and be asked for the urine samples. Following the study, the control group will be able to access the intervention and have access to the study team for support.

The Link for the intervention videos is below:

<https://drive.google.com/drive/folders/1aGv-d85VnuriTcta9dkRt6OjizcMHRf2?usp=sharing>

4. Analysis

Describe any qualitative tests and measures as well as quantitative methods:

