Writing Exposures (four virtual sessions). Based on a previous internet-based protocol, we will integrate writing exposures to treat participants' most significant fears (note that fears naturally occur in nearly all persons in the population even if the participant is not above clinical levels of anxiety). First, we will include a brief rationale for engaging in exposure therapy. Participants will then be asked to write about the nature of fears in detail, describing intimate fears and thoughts, writing in the first person and in present tense, relating olfactory, visual, and auditory sensations. The goal of this work is to provide a transdiagnostic ability to treat a variety of fears (e.g., this could target fears related to trauma, social anxiety, or interoceptive fears). **Cognitive-Reappraisal (four virtual sessions).** Participants will be educated about common principals of cognitive reappraisal in order to instill new insights. Participants will be asked to include positive aspects of trauma and aversive

experiences on their lives. Participants will also be asked to restructure their own thoughts. The platform will send reminder texts and emails when it is time to complete the new session. Additionally, the platform will also send targeted texts and emails to users who have not completed the intervention two days later and send a third text message and email asking if they were having any difficulty in accessing the intervention if they have not completed the intervention within three days after the scheduled time. **Qualitative Feedback.** In order to further refine the digital intervention, qualitative feedback on the digital intervention will also be solicited. This will include the participant's level of satisfaction with the intervention, perceived benefits, and recommended modifications, combining both Likert and open-ended feedback. **Refinement.** Following the conclusion of the study, the qualitative feedback and usage patterns will be used to further refine the intervention.

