Analyses. To test feasibility for **Hypothesis 1**, we will determine whether we can achieve the targeted enrollment ($N = 80$) and whether the average number of digital sessions is significantly higher than 50% based on multilevel binomial test nesting individual session completion rates within persons. To test **Hypothesis 2**, the current proposal will use intent-to-treat analyses employing multilevel modeling to examine moderation of change across time from pre to post, and post to follow-up. Based on power analyses, we will be well-powered to test the effects of the intervention (3-5 data points per person \times 80 participants = 180-300 \times 80% adherence = 144-240 data points total).

5. Study Progress Monitoring

Note: appropriate monitoring may include periodic assessment of the following:

- data quality
- timelines
- recruitment and enrollment

Provide a description of the methods which will be used to determine the progress of the study, including periodic assessments of data quality, timelines, recruitment, and enrollment as appropriate:

Recruitment. A population of 3000 adults who are receiving medication treatment for OUD will be recruited from an online study based on Google Adwords advertisements as online recruitment has been shown to be a viable and cost-effective recruitment method for opioid users (Marshall et al., 2018). We are only recruiting from the US.

We will also recruit via Reddit forum as well. Please see the document with the example of the post we would be planning on using.

Six opioid-focused subreddits were initially identified. Subreddits were selected based on their topical focus and their popularity. All were devoted to discussion of opioid use or recovery. In September 2019, the number of Redditors subscribed to each subreddit ranged from 4,000 to 82,000 people. Each subreddit was monitored by multiple moderators, who ensured all posts follow the Reddit community guidelines and remain focused on the topic of interest. All moderators in each of the six subreddits will be contacted by the study team to obtain approval to post the survey description and hyperlink. Moderators will be sent a study information sheet and a link to view the study description.

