Clinical Expertise. All research will be overseen by [name] who has a doctorate in clinical psychology.

Availability of the Study Team. [name] will be available to discuss the study or any concerns about the study with participants if requested by the participant. [name] will be available in the event of a clinical emergency, and this availability will be clearly communicated orally and in writing to study participants. Participants will be provided information such as how to reach the investigators in the event of a clinical emergency. Participants will be referred to a treatment resource or a higher level of care if needed (i.e., hospitalization). Participants will be referred to a higher level of care if there is evidence of (1) acute active suicidality with a plan and intent to take one's life within a delineated period of time (i.e. less than 1 year), (2) acute homicidally with a plan or intent to take another's life, or (3) likelihood that they could immediately cause severe bodily harm to themselves or others (see **Clinical Referrals below**).

Ability to Withdraw. Participants may be able to withdraw from the study due to a significantly deteriorating course (e.g., need for hospitalization) or if the PI or participant determines that staying in the study is not in the participant's best interest. All participants who withdraw will be provided referrals for treatment.

Clinical Referrals. All participants will be given the phone number for the National Suicide Prevention Hotline, which is funded by the Substance Abuse and Mental Health Services Administration (SAMHSA). The hotline is staffed 24/7 by licensed mental health providers and is available throughout the United States. For persons not in acute risk who need a referral to outpatient treatment, we will identify referral sources using the Anxiety and Depression Association of America (ADAA), the Association for Behavioral and Cognitive Therapies (ABCT), the American Psychiatric Association, and the American Psychological Association. Each of these organizations maintains an active registry of current psychologists and psychiatrists across the country, many of whom provide the ability to also specify persons specializing in treating anxiety and depression.

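### Hypothesis 1 is about the average share of 16 sessions completed, but its multilevel binomial test has no stated model and, run in the usual way, can mislead about that average if completion is markedly skewed

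*Combined protocol and SAP*

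**What the plan says.** Section 2 (Objectives and Hypotheses, Hypothesis 1) sets the acceptability criterion as "greater than 50% of the intervention sessions completed on average by the treatment group". Section 3 (Study Design, Main Study) fixes the schedule at four sessions a week for four weeks, 16 in all.

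Section 4 (Analysis, the Analyses paragraph) will determine "whether the average number of digital sessions is significantly higher than 50% based on multilevel binomial test nesting individual session completion rates within persons". It gives no link function, random-effect distribution, tested parameter, alpha or sidedness. The same paragraph's intent-to-treat statement belongs to Hypothesis 2: "the current proposal will use intent-to-treat analyses employing multilevel modeling to examine moderation of change across time".

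Missed sessions are foreseen, since the platform sends "targeted texts and emails to users who have not completed the intervention two days later". Withdrawal is also allowed (section 6, Ability to Withdraw): "Participants may be able to withdraw from the study due to a significantly deteriorating course". No section says in terms how sessions scheduled after withdrawal are counted.

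**The concern.** The hypothesis is about a mean over people of a proportion. A multilevel logistic model has as its natural parameter the intercept, which is the mean of people's log-odds. An intercept of zero and a mean share of 50% coincide when the log-odds are spread symmetrically about zero, but not in general. People who complete nearly everything, or nearly nothing, have extreme log-odds and pull the intercept much further than they pull the mean share.

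At stake is the claim of significantly more than 50% completion, which is the acceptability half of Aim 1. The observed mean itself is unaffected, as are Hypothesis 2 and safety.

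**Working it through.** The plan gives no power figure, alpha or error rate for Hypothesis 1, so there is nothing to reproduce.

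**Inputs from the documents.** Sessions per person: 4 × 4 = 16. Treatment-arm size: 40 in Hypothesis 1. Aim 2 gives 30, so both sizes were run.

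**Assumptions.** One-sided 5%. Random-intercept logistic model with normal random effects, signed likelihood-ratio test of intercept = 0. Comparator: one-sample t-test of completed/16 against 0.50. All completion patterns are assumed. Sessions not done count as not completed.

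**Step 1: why skew matters.** Compare the mean share with the mean log-odds, where logit(p) = ln[p/(1 − p)].

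- 40% of people at 95%, 60% at 20%. Mean share: 0.4 × 0.95 + 0.6 × 0.20 = 0.50. Mean log-odds: 0.4 × 2.944 + 0.6 × (−1.386) = +0.35.
- One third at 98%, two thirds at 26%. Mean share: 0.327 + 0.173 = 0.50. Mean log-odds: 3.892/3 − 2 × 1.046/3 = +0.60.
- 60% at 80%, 40% at 5%. Mean share: 0.48 + 0.02 = 0.50. Mean log-odds: 0.6 × 1.386 − 0.4 × 2.944 = −0.35.
- Milder: 40% at 80%, 60% at 30%. Mean share: 0.32 + 0.18 = 0.50. Mean log-odds: 0.4 × 1.386 − 0.6 × 0.847 = +0.05.

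In the first three patterns the mean is exactly 50% but the intercept's target is well away from zero.

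**Step 2: error rates by simulation** (4,000 trials per pattern, n = 40, true mean 50%; share of trials that wrongly find more than 50%).

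| Pattern | Multilevel logistic | t-test |
|---|---|---|
| Logit-normal | 6% | 5% |
| Uniform | 5% | 5% |
| U-shaped | 6% | 5% |
| 40% at 80%, 60% at 30% | 6.5% | 5% |
| Steady dropout, active users miss 10% | 4.5% | 4% |
| Steady dropout, active users miss 5% | 7% | 5% |
| Steady dropout, no other misses | 12% | 5% |
| 40% at 95%, 60% at 20% | 18% | 4% |
| One third at 98%, two thirds at 26% | 28% | 4% |
| 60% at 80%, 40% at 5% | 2% | 5% |

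In the last pattern the logistic test wrongly finds less than 50% in 19% of trials, against 4%. With n = 30, the 40/60 mix at 95%/20% gives 15% against 4%, and the one-third/two-thirds mix 23% against 4%.

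**Step 3: power.** With 75% of people at 78% and 25% at 5%, the mean is 0.585 + 0.0125 ≈ 60%. Power is 35% for the logistic test and 58% for the t-test (n = 40).

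**Step 4: two worked data sets, n = 40.**

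- 18 people do all 16 and 22 do 2 to 5 (75 sessions in total). Mean = (288 + 75)/640 = 56.7%, 95% CI 44 to 70. Logistic p = 0.004; t-test p = 0.15.
- 12 people do none and 28 do 12 to 14 (364 sessions). Mean = 364/640 = 56.9%, 95% CI 45 to 69. Logistic p = 0.66; t-test p = 0.13.

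The two means are almost equal, and the logistic test gives opposite answers.

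**Step 5: the counting rule, for illustration.** Suppose 20% withdrew, equally likely after 0 to 15 sessions; 20% is an assumption, not a figure in the documents. The mean share elapsed at withdrawal is 7.5/16 = 0.469. A true 50% of the 16 sessions then reads as 0.50/(0.80 + 0.20 × 0.469) = 0.50/0.894 = 56% if later sessions are left out.

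**The case against.** The plan does say what is tested: the average, in both section 2 and section 4. A reader might infer that it tests the wrong quantity; it does not. What is missing is how the named test delivers that average. The normal-intercept logistic model is my assumption, and a clustered binomial test of the population mean would also fit the wording. That stands: the criticism applies to the usual implementation, not to something the plan commits to.

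Material harm also needs an unusual shape, a large near-perfect group beside a low-use group or the reverse. Step 2 shows many plausible patterns at or near 5%, and the reminders suggest that active users will miss some sessions. This also stands, and it is why no claim is made that the error will occur.

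On counting, an undone online session is naturally recorded as not completed, and Hypothesis 1's wording with its 16-session schedule already points that way. A reader might infer that withdrawn people's later sessions will be dropped; nothing in the plan says so. A reader might also take a 20% withdrawal rate from "80% adherence = 144-240 data points total". That 80% multiplies assessment data points for Hypothesis 2. It is neither a session-completion rate nor a withdrawal rate.

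None of this removes the case for the change: the proposed test addresses the same average and, in every pattern tried, stayed close to its nominal error rate.

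**Conclusion.** The point holds in a conditional form. The test for Hypothesis 1 is under-specified. In its usual form it is valid for symmetric or mildly skewed completion but unreliable about the average under marked skew. The size, at n = 40 and one-sided 5%, is a false-positive rate of about 18 to 28% instead of 4 to 5% in one direction, and power of 35% instead of 58% at a true 60% in the other. These figures rest on the assumed model and assumed patterns. A reader might infer that the acceptability result will be falsely positive; the documents give no completion distribution, so neither the presence nor the direction of the error can be predicted. The counting rule, alpha and sidedness are clarifications. This is a worthwhile, inexpensive improvement, not a demonstrated flaw in the result.

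**What to change.** In the Analyses paragraph of section 4, define the outcome for every participant randomised to the intervention as sessions completed / 16. Test the mean of these shares against 0.50 at participant level, by one-sample t-test, bootstrap, or a marginal mean with robust standard error. State alpha and sidedness, and that sessions not done, including those after withdrawal, count as not completed. Report the mean with its 95% CI and the distribution of sessions completed. Keep the multilevel model as a description of completion.

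The change is wording only; no data collection is affected. The cost is a little power if the multilevel model's assumption is true. With logit-normal use (SD 2) and n = 40, power is 61.5% against 63% at a true 60%, and 89% against 90.5% at a true 65%. With n = 30 it is 49% against 51%, and 80% against 82%. The loss is about 1 to 2 points at n = 40 and 2 to 3 at n = 30.

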Inclusion Criteria. (a) Adults (age 18 or older), (b) fluent in English, (c) able to provide informed consent, (d) meet current criteria for OUD (as defined by a Rapid Opioid Dependence Screen), (e) are receiving methadone, buprenorphine, and/or naltrexone for OUD, and (f) meet current criteria for an anxiety and/or depressive disorder (based on the Patient Health Questionnaire and the Generalized Anxiety Disorder Questionnaire).

Procedure.

Screening: Participants will complete the Initial Consent form, giving the study team permission to collect survey answers to the PHQ-9, GAD, Opioid Craving Scale, and RODS as well as contact information. If eligible the participants will move on to the main consent form stage.

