13. Financial impact on participants

a. List the tests, visits, and procedures performed for only research purposes and specify who will pay:

Note: Research procedures may not be billed to a health insurance plan

Participant Recruitment. A total of \$3,000 will be spent on online participant recruitment in the US only. We estimate a total cost of \$10 per participant to recruit 3000 participants, with an estimated enrollment of 2% of persons who complete the screen will enroll in the primary portion of the study.

Precision Dx 12-panel Urine Tests. The Precision Dx 12 Panel Cup test cups will cost a total of \$2,250.00 to purchase (we will need to purchase 300 units, with 25 units per case, we will need to purchase 12 cases with each case costing \$187.50). To save on shipping costs, the five tests will be mailed together to participants in one box. Participants will be asked to send a picture of the results label to save on shipping costs and so that no bodily fluids are traveling via mail. There will be an estimated \$720 in shipping costs.

Participant Remuneration: Participants will be paid \$15 for each pre, post, and follow-up questionnaire assessment and \$15 for each urine test (totaling \$120 per participant). Thus, the total cost requested for participant payment is \$7,200.

14. Compensation or Gifts

Please describe any payments, gifts or reimbursements participants will receive for taking part in the study:

Participants will be compensated via amazon giftcard for each component of the study they complete. They will receive 15 dollars for each questionnaire assessment they complete along with 15 dollars for each completed urine test. Compensation will be pro-rated if participants forget to complete any part of the study: The following information lays out the time points that participants will be compensated. Participants will not be compensated for completing the screening questionnaires.

Before the Digital Intervention: 30 dollars total

- 1) \$15 dollars for completing the self-assessment survey
- 2) \$15 dollars for providing the first urine (after 0 weeks) sample results.

After the Intervention is completed: 45 dollars total

- 1) 15 dollars for completing the post-intervention questionnaire
- 2) \$15 dollars for providing second urine sample (after 2 weeks)
- 3) \$15 dollars for providing third urine sample (after 4 weeks)

At the one-month follow-up: 45 dollars total

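### As most naturally read, the Hypothesis 2 model tests a change score at week 4, which uses the baseline score validly but not as efficiently as a baseline-adjusted comparison would

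*Combined protocol and SAP*

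**What the plan says.** The only analysis text for Hypothesis 2 is one sentence in Section 4 (Analysis), under Analyses: "intent-to-treat analyses employing multilevel modeling to examine moderation of change across time from pre to post, and post to follow-up". It lists no fixed effects and no covariance structure, and does not say how the baseline score enters. Baseline adjustment is not mentioned anywhere else in the document.

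Four other places bear on the point:

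- Section 2 states Hypothesis 2 as a larger fall in symptoms with the intervention and "decreased opioid cravings and use across a four-week period".
- Section 3 (Main Study) places the baseline questionnaires ahead of allocation: "Participants will complete self-report assessments on their anxiety symptoms, depressive symptoms, opioid cravings, and opioid use behaviors", and after that "Participants will be randomized to a smartphone-based digital intervention or waitlist control condition".
- Section 13 pays "for each pre, post, and follow-up questionnaire assessment", so each questionnaire score has three planned occasions.
- The inclusion criteria (Sections 3, 5 and 10c) require that participants "meet current criteria for an anxiety and/or depressive disorder (based on the Patient Health Questionnaire and the Generalized Anxiety Disorder Questionnaire"). The craving score is not an entry criterion.

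**The concern.** Examining whether arm moderates change from pre most naturally means arm, time and arm-by-time terms, with the pre score as one of the outcome rows. Each arm then has a free baseline mean. With complete data, the arm-by-time term for pre to post is exactly the difference between arms in mean change.

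Randomisation makes the two baseline means equal in expectation. A model that uses this fact, or that takes baseline as a covariate, estimates the weight given to baseline instead of fixing it at 1. In a trial of this size the difference can be worth several power points, from data the plan already intends to collect.

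**Working it through.** **The plan's own figure.** The power statement in Section 4 multiplies 3-5 data points by 80 participants and reports 180-300, then 144-240 after 80% adherence. In fact 3-5 × 80 = 240-400, while 3-5 × 60 = 180-300 and × 0.8 = 144-240. The figures therefore match 60 participants, and Section 2 carries both 40 and 30 per arm. Both sizes are shown below. No power, alpha, effect size, SD or correlation is stated, so no power figure can be reproduced.

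**Assumptions, none from the documents.** True effect 0.5 SD of the post score; two-sided 5%; rho 0.4, 0.5 or 0.7; k = baseline SD / post SD of 1, 0.8 or 0.7. Values of k below 1 are included because entry on PHQ and/or GAD criteria may narrow the baseline spread of those scores.

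**Variances.** With post SD 1, per unit of 2/n:

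- free baseline means (change score): k² + 1 - 2·rho·k
- baseline-adjusted: 1 - rho²
- difference: k² - 2·rho·k + rho² = (k - rho)², which is never negative and is zero when k = rho.

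Example, k = 1 and rho = 0.4: 1 + 1 - 0.8 = 1.20 against 1 - 0.16 = 0.84, a ratio of 1.43. Example, k = 0.7 and rho = 0.4: 0.49 + 1 - 0.56 = 0.93 against 0.84, a ratio of 1.11.

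| k | rho 0.4 | rho 0.5 | rho 0.7 |
|---|---|---|---|
| 1 | 1.20 / 0.84 = 1.43 | 1.00 / 0.75 = 1.33 | 0.60 / 0.51 = 1.18 |
| 0.8 | 1.00 / 0.84 = 1.19 | 0.84 / 0.75 = 1.12 | 0.52 / 0.51 = 1.02 |
| 0.7 | 0.93 / 0.84 = 1.11 | 0.79 / 0.75 = 1.05 | 0.51 / 0.51 = 1.00 |

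**Power of the week-4 test in the three-occasion model.** This is generalised least squares with known covariance: equal correlation rho; SDs k, 1, 1; baseline complete; post and follow-up each observed with probability 0.8 at random. The t reference has 62 df (40 per arm) or 46 df (30 per arm). Entries are free means v common baseline mean.

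| Randomised per arm | k | rho 0.4 | rho 0.5 | rho 0.7 |
|---|---|---|---|---|
| 40 | 1 | 46% v 58% | 53% v 63% | 74% v 80% |
| 40 | 0.7 | 55% v 58% | 61% v 63% | 80% v 80% |
| 30 | 1 | 36% v 46% | 42% v 51% | 61% v 67% |
| 30 | 0.7 | 43% v 46% | 49% v 51% | 67% v 67% |

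The gain is about 6 to 12 points at k = 1 and 0 to 3 points at k = 0.7.

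**Cost of estimating the slope.** Simulated change-score and covariate analyses (40,000 trials per cell) both average the true 0.50. Under the null (60,000 trials, rho 0.5) both reject in 4.9% to 5.1%. In the worst simulated case for adjustment, k = rho = 0.7, its power is 78.4% against 79.1% for the change score at 32 per arm, and 65.2% against 66.3% at 24 per arm.

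**Covariance form.** A common baseline mean with only a random intercept forces equal variances across occasions. With two occasions its implied slope is b = rho·k / ((k² + 1)/2), and its variance is 1 + b²k² - 2·b·rho·k. At k = rho = 0.7, b = 0.49/0.745 = 0.658 and the variance is 0.567, against 0.51 for the change score. That is about 11% worse, so the covariance must be stated together with the adjustment.

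**The case against.** A reader might infer that the planned test ignores baseline or gains no precision from it. That is not so. A change score subtracts baseline with weight 1. Against a post-only comparison (variance 1), it is more precise in six of the nine cells in the variance table, equal in two and worse in one (k = 1, rho = 0.4). A reader might also infer a biased four-week test, or a misuse of the post-to-follow-up term as evidence of lasting benefit. The documents support neither: the contrast is unbiased, it matches the way Hypothesis 2 is worded, and the plan makes no such claim for the later term.

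The strongest objections are these:

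- **The reading is inferred.** One sentence without an equation does not exclude a common-baseline model. This stands. If such a model was intended, the plan still needs to say so.
- **The gain rests on assumed values.** This stands. It may be close to nil for the PHQ and GAD scores if entry selection narrows their baseline spread. Craving is not an entry criterion, so its baseline spread is not directly narrowed in this way.
- **Adjustment is not entirely without risk.** This stands, in the two forms shown in the working: about 1 power point in the worst simulated case, and a real loss if the covariance is a random intercept alone.
- **Baselines may be missing.** Section 4 applies its 80% to every data point and Section 14 anticipates missed components. A plain covariate model would drop anyone without a baseline. Because assessment is described before randomisation the risk is modest, but the remedy should cover it.
- **Not every score is clearly continuous.** Section 4 describes the GAD-Q-IV in diagnostic terms and gives no continuous scoring. The point is therefore limited to scores analysed as continuous, and does not extend to the binary urine results.

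**Conclusion.** The point holds as one of efficiency and specification; it does not show an error. On the natural reading, the week-4 test has variance (k - rho)² above that of a baseline-adjusted test in post-SD units, before the small cost of estimating the slope. Under the stated assumptions this is worth about 6 to 12 power points if baseline and post spreads are equal, and about 0 to 3 points at k = 0.7. The documents cannot settle which applies, because they give no rho, SD or effect size. Sample size remains the main limit on precision.

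The one-month comparison is not part of the defect. Section 3 says "Both the digital intervention group and the control group will receive the same follow-up assessments", so it can be estimated from the planned model as the sum of the two arm-by-time terms.

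**What to change.** Keep the intent-to-treat multilevel model and add to Section 4, in advance:

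1. For scores analysed as continuous, such as the PHQ-9 and cravings, Hypothesis 2 is tested by the baseline-adjusted arm difference at week 4.
2. Preferably, the arms share a common baseline mean and the covariance over the three occasions is unstructured, not a random intercept alone. This also keeps participants with a missing baseline. A baseline covariate is an acceptable alternative if the plan says how missing baselines are handled.
3. Optionally, report the baseline-adjusted arm difference at one month with its 95% CI beside the post-to-follow-up term.

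The cost is a few sentences of analysis text, including a covariance choice on which the plan is now silent. No new data, extra participants or change of model class is needed.
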